Please note that Epidiolex is FDA approved for the treatment of seizures in Lennox-Gestaut syndrome and Dravet syndrome and is clinically used for the treatment of seizures in Sturge-Weber syndrome and many other medically refractory seizure disorders[1-3]. Epidiolex is **no longer** scheduled and can be prescribed clinically for patients seen remotely. We are studying Epidiolex here in Sturge-Weber syndrome for different indications.

Hypothesis: Cannabidiol (Epidiolex) improves SWS brain function resulting in improved cognitive function, social interactions, mood, motor function and behavior, as well as reduced migraines.

2. Objectives (include all primary and secondary objectives)

We propose a follow up to the initial SWS Epidiolex study which suggested improvements in SWS cognitive, social, and behavioral function and in other neurologic issues. **Primary outcome measure:** Quantify cognition 6 months after initiation of Epidiolex compared to baseline. **Secondary outcome**

measures: The following at 6 months compared to baseline: Social function and mood, frequency and severity of seizures, migraine frequency and severity, and motor outcomes.

3. Background (briefly describe pre-clinical and clinical data, current experience with procedures, drug or device, and any other relevant information to justify the research)

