Final Evaluations: Done on or close to Visit 5 (within a 7-day period of time) and while still on Epidiolex. Cognitive testing/assessments: 1 1/2 hours. Psychiatric/Mood: 1 hour. Neurologic Exam, history, picture, neuroscore, birthmark score: 1 hour. Labs: 30 minutes. Total=4 hours.

Outcome Measures

Primary Outcome Measure: *The primary outcome* will be a **change in cognitive function** defined as change in score on the List Sorting Working Memory test. This cognitive test in the NIH Toolbox was suggested by our data in another study to yield the most actionable data. The NIH has provided guidance on the remote application of the NIH Toolbox Changes in cognitive function (from pre-treatment baseline to 6 months on study drug) will be assessed. Each subject measured at baseline will serve as his/her own control. Other cognitive function tests (below) which will be measured were selected because they also assess working memory and processing speed.

The NIH Toolbox for the Assessment of Neurological and Behavioral Function (NIH-TB).[26 27] Cognitive measures are computer-based tasks used for assessing a number of cognitive domains, including executive functioning, memory, language, etc. Because the tests were developed and normed for use with a very broad age range (ages 3-89), the NIH-TB is appropriate for the range of ages proposed for this research application (childhood, adolescence, and early adulthood). The NIH-TB has also been shown to be appropriate for use with individuals with lower or impaired cognitive functioning.[28] These are published tests which are widely used. From amongst the measures of the NIB-TB Cognitive measures, two measures were selected for use both which we have already utilized in subjects (and patients) with SWS:

The List Sorting Working Memory subtest is a test of working memory which will be used to assess the study outcome of working memory. Approximate time: 10 minutes

Secondary Outcome Measures

Change in other cognitive outcomes: The Picture Vocabulary subtest is a single-word receptive vocabulary/auditory comprehension task. When administered: Single words are presented via an audio file, paired simultaneously with 4 screen images of objects, actions, and/or depictions of concepts. The task is to pick the picture that matches the spoken word.77 This subtest was selected as one less likely to be treatment responsive, as compared to the other two above. Approximate time: 10 minutes

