An earlier study of Epidiolex for medically refractory seizures in Sturge-Weber syndrome suggested improvement in cognition, social, and behavioral outcomes. The side effects experienced were mild and transient.

The proposed trial will be assessing the impact of Epidiolex upon cognitive impairment in Sturge-Weber patients.

c. Justification and safety information if non-FDA approved drugs without an IND will be administered.

Not applicable.

7. Study Statistics

a. Primary outcome variable.

Change in cognitive impairment: Combined score of two NIH Toolbox subtests.

b. Secondary outcome variables.

Change in the following:
SWS neuroscore
Port-wine score
Adverse Events
Seizure severity
Social, behavioral, and mood function
Migraine severity
Motor function

c. Statistical plan including sample size justification and interim data analysis.

Statistical Plan: Results of the above tests will be compared to age normed values. In addition, the difference in results between final test results and initial test results will be obtained for the cognitive functioning score of each subject. Mean and standard deviation of this difference for all 10 subjects on study drug will be calculated. These results will be used to determine whether individuals and the group as a whole demonstrated age normed changes in their cognitive functioning over the course of the six month trial. There is no control group in this study of subjects who are not receiving study drug. The published test-retest standard deviations will be used to determine whether changes in testing results exceed expected test-retest changes in results.

Sample Size Calculation: Since these outcomes will be done for the first time with this drug in SWS, a sample size calculation was not done. Rather, we are estimating that 10 subjects enrolled and on study drug will be sufficient to do the proposed pilot trial and show improvements (or trends for improvement) sufficient to design a future larger clinical trial, or to guide clinical care. This estimate is based on our experience with another trial using the same primary outcome measure.

Interim data analysis: Every week [name] and the study coordinator study will review data for safety. Each month, a formal review of recruitment, safety, data completion and study progress will be made. An

assessment of progress as it relates to study milestones (see **Milestone Table** below) will be made, and a summary report prepared for Greenwich Biosciences.

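### The primary outcome has two incompatible definitions: List Sorting Working Memory alone in Section 4a, an unspecified two-subtest composite in Section 7a

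*Combined protocol and SAP*

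**What the plan says.** In Section 4a, under Outcome Measures, the primary outcome is a change in cognitive function "defined as change in score on the List Sorting Working Memory test", from pre-treatment baseline to 6 months on drug. In Section 7a the primary outcome variable is "Change in cognitive impairment: Combined score of two NIH Toolbox subtests".

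The other relevant places do not settle the matter:

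- Section 2 (Objectives) says only "Quantify cognition 6 months after initiation of Epidiolex compared to baseline".
- Section 4a, on the NIH Toolbox, says that "two measures were selected for use both which we have already utilized in subjects (and patients) with SWS", but List Sorting is the only one described directly after that statement.
- Picture Vocabulary is the only other Toolbox cognition subtest described. It appears under Secondary Outcome Measures with the remark "This subtest was selected as one less likely to be treatment responsive, as compared to the other two above". Only one subtest is described above it.
- Section 7c says that the difference between final and initial results "will be obtained for the cognitive functioning score of each subject", without tying that score to a test.
- Section 7c also sets the yardstick: "The published test-retest standard deviations will be used to determine whether changes in testing results exceed expected test-retest changes in results". No value, source, score type or cut-off is given.
- The sample size paragraph in Section 7c says: "This estimate is based on our experience with another trial using the same primary outcome measure".

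**The concern.** A single test and a composite of two tests are different variables, with different means, different variances and different test-retest SDs. Section 7c promises a judgement on individual subjects and on the group against published test-retest SDs. Such an SD belongs to one particular score, so until the score is fixed the benchmark cannot be looked up.

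The trial is open-label and single-arm, and Section 7c schedules an interim analysis that includes outcome measures. With both definitions standing, the primary could be chosen after results are known. Section 7c says the results may help design a larger trial or guide clinical care, so even a pilot needs one named primary.

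If the second subtest is Picture Vocabulary, the composite would include a measure that the plan itself expects to respond less. An effect on List Sorting could then be diluted.

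**Working it through.** **Step 1. The two definitions side by side.**

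| Item | Section 4a | Section 7a |
|---|---|---|
| Variable | Change in List Sorting | Change in a combined score |
| Subtests | One, named | Two, not named |
| Score type | Not stated | Not stated |
| Combination rule | Not needed | Not stated |
| Time points | Baseline and 6 months | Not stated |
| Matching test-retest SD | Not stated | Not stated |

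The components of the composite might be guessed as List Sorting and Picture Vocabulary, the only two Toolbox subtests described. That guess conflicts with Picture Vocabulary being listed as secondary, and with the remark that contrasts it with two earlier tests when the text describes one.

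The plan gives no SD, effect size, alpha or power, and says no sample size calculation was done. There is no plan figure to reproduce, and the rest of this working is illustration under stated assumptions.

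**Step 2. The plan's own kind of benchmark.** Assume both subtests have the same test-retest SD of change, S, that the composite is their mean, and that the two test-retest changes correlate r, from 0 to 0.7.

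- SD of the composite change = S × √((1 + r)/2).
- Subject A gains 2S on List Sorting and 0 on the other test. The composite change is (2S + 0)/2 = 1S.
- Subject B gains 2S on both. The composite change is 2S.
- On List Sorting alone both subjects stand at 2S/S = 2.0.

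| r | Composite SD | Subject A, in composite SDs | Subject B, in composite SDs |
|---|---|---|---|
| 0 | 0.707S | 1.41 | 2.83 |
| 0.3 | 0.806S | 1.24 | 2.48 |
| 0.5 | 0.866S | 1.15 | 2.31 |
| 0.7 | 0.922S | 1.08 | 2.17 |

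At any cut-off between 1.41 and 2 SD, the two definitions disagree about subject A throughout this range of r. If the composite were judged against S, the List Sorting SD, instead of its own SD, subjects A and B would read 1.0 and 2.0. The choice of SD therefore matters as well as the choice of score.

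**Step 3. A group-level illustration.** The plan names no hypothesis test. Suppose a paired t-test were used with n = 10, two-sided 5%, equal weights and equal SDs of change, and List Sorting truly gained 0.8 SD. The standardised effect of the composite is the mean of the two effects divided by √((1 + r)/2).

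- Second test unresponsive: 0.40/0.707 = 0.57 at r = 0, and 0.40/0.922 = 0.43 at r = 0.7. Power falls from 62% for List Sorting alone to 36% and 23%.
- Second test responds equally: 0.80/0.707 = 1.13 and 0.80/0.922 = 0.87. Power becomes 89% and 69%.

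Simulation gives the share of trials in which exactly one definition is significant (400,000 trials per cell). It also gives the chance that at least one is significant when there is no true effect (1,000,000 trials per cell).

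| r | Discordant, second test unresponsive | Discordant, second test responds equally | Either significant, no true effect |
|---|---|---|---|
| 0 | 0.339 | 0.305 | 0.085 |
| 0.3 | 0.356 | 0.238 | 0.080 |
| 0.5 | 0.370 | 0.191 | 0.075 |
| 0.7 | 0.386 | 0.140 | 0.070 |

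A single pre-specified version would have a false-positive rate of 0.050.

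**Step 4. Timing.** The document is dated 29 June 2021. The milestone table places an interim analysis of subjects 1 to 5, with a go/no-go decision, under February 2020, and completion of data analysis under September 2021. If the interim took place as scheduled, outcome data were seen before this text was dated. The document does not say whether it did.

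**The case against.** The strongest reply is that Section 4a is the detailed text and should govern. It names the test, the two time points and a rationale, and Section 7c partly points to the score type by mentioning age-normed values. On that reading the score is nearly settled and only its exact type and SD are missing. This stands as far as it goes: the benchmark is better called not uniquely determined than wholly undefined. But the plan has no rule of precedence, and Section 7a is where the statistics section names its primary variable.

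A second reply is that this is an uncontrolled pilot with no planned hypothesis test, meant partly to find the best outcome measures for a later randomised trial. That is fair, and it limits Step 3 to illustration. Those figures also depend on an assumed 0.8 SD effect and reflect the imprecision of ten subjects. Step 2 is closer to the plan, although its subjects are constructed and the plan gives no cut-off. The conflict between the two sections depends on neither step.

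A third reply is that the choice of ten subjects was a judgement, so no number changes with the definition. That is correct. What remains is that the justification appeals to a shared primary outcome measure without saying which one.

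**Conclusion.** The concern holds. Sections 4a and 7a name different primary variables in current text, and no other section resolves the conflict. This is a contradiction in the plan, beyond any missing detail, and it must be corrected before the final analysis.

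The consequence cannot be sized from the plan alone. Under equal test-retest SDs, equal weights and correlations of 0 to 0.7, the same subject can read 2.0 SD under one definition and anywhere from 1.1 to 2.8 SD under the other, depending on how the second test behaves. If a paired t-test were used and List Sorting truly gained 0.8 SD, the definitions would disagree in 34 to 39% of trials with an unresponsive second test, and in 14.0 to 30.5% with an equally responsive one. Freedom to report either version would raise a 5% false-positive rate to between 7.0 and 8.5%.

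**What to change.** Issue one dated, justified amendment before the final analysis:

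1. State one primary variable and use it in Sections 2, 4a, 7a and 7c. Change in List Sorting Working Memory from baseline to 6 months, with the score type stated (for example age-corrected), is the natural choice because only that version has a named test and a rationale.
2. If a composite is kept, name both subtests, the score type, the combination rule and the source of the composite's test-retest SD.
3. In Section 7c, replace the generic cognitive score with the named score, and give the test-retest SD that belongs to it, its source and the cut-off for change.
4. List the remaining cognitive tests in Section 7b, which omits them, and remove the wording in the WISC-V paragraph of Section 4a that describes its subtests as measuring primary outcomes.
5. In the sample size paragraph, say which measure the earlier trial used.
6. State whether any outcome data, including the interim on subjects 1 to 5, had been seen when the choice was made. If they had, the amendment removes the ambiguity but cannot restore pre-specification, and the report should say so.

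The cost is a wording change. List Sorting is already planned at baseline and 6 months, so the Section 4a version needs no new data or visits.

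### With no control group, change on drug is judged only against published test-retest SDs, with no stated allowance for an average retest gain

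*Combined protocol and SAP*

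**What the plan says.** The Outcome Measures part of section 4a takes change from baseline to six months on drug as the primary comparison and says "Each subject measured at baseline will serve as his/her own control". Section 7c computes final minus initial score for each participant, then the mean and SD of that difference over the 10 on study drug. It continues: "These results will be used to determine whether individuals and the group as a whole demonstrated age normed changes in their cognitive functioning". It confirms that "There is no control group in this study of subjects who are not receiving study drug", and then gives the yardstick: "The published test-retest standard deviations will be used to determine whether changes in testing results exceed expected test-retest changes in results".

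Section 7c does not give:
- a value or a source for the published SD;
- whether it is an SD of retest differences or a standard error of measurement;
- how many SDs count as change;
- whether an average retest change is subtracted.

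The score that the SD belongs to is also unsettled. Section 4a has the primary outcome "defined as change in score on the List Sorting Working Memory test", while section 7a has "Combined score of two NIH Toolbox subtests".

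**The concern.** People can score differently the second time they take a cognitive test, on average as well as individually. An SD of retest change covers the individual scatter and says nothing about the average shift. Comparing scores with age norms removes what is expected from being six months older. It does not remove what comes from having seen the test before. In a controlled trial the comparison arm would absorb such a shift; here nothing does unless the analysis subtracts it.

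If there is an average retest gain, the rule as written leaves it in the change score, where it looks like a drug effect. Section 7c intends the results to help design a larger trial or to guide clinical care, and the Milestone Table in section 7d lists grant applications after the analysis. An effect that is partly retest gain would carry into those uses.

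**Working it through.** **No figure to reproduce.** The plan states no alpha, effect size, SD, cut-off or retest gain, and section 7c says that no sample size calculation was done. What follows shows sensitivity only.

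**Inputs.** From the documents: n = 10, no control group, baseline and six-month scores. Assumed: normally distributed changes, an inert drug, an average retest gain g of 0 to 0.5, and a multiplier of 1.96. The unit is the SD of retest differences.

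**Group, if the rule is applied to the mean.** Suppose the mean change is held against 1.96/√10 = 0.62 SD. The chance that it is exceeded is 1 − Φ(1.96 − g√10).

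| Assumed gain g | 1.96 − g√10 | Chance of exceeding |
|---|---|---|
| 0 | 1.960 | 2.5% |
| 0.2 | 1.328 | 9.2% |
| 0.3 | 1.011 | 15.6% |
| 0.5 | 0.379 | 35.2% |

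With no gain the rule holds its nominal upper tail. The excess comes entirely from the gain that is not subtracted.

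**Individuals, cut-off 1.96 SD.** The chance per participant is p = 1 − Φ(1.96 − g), the expected number is 10p, and the chance of at least one is 1 − (1 − p)^10.
- g = 0: p = 2.5%, so 0.25 of 10 expected; at least one, 22%.
- g = 0.5: p = 7.2%, so 0.72 of 10 expected; at least one, 53%.

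**If the published figure is a standard error of measurement (SEM).** The SD of a difference is then √2 × SEM, so a cut-off of 1.96 SEM is only 1.96/√2 = 1.386 SDs of the difference. With no gain, p = 1 − Φ(1.386) = 8.3% per participant instead of 2.5%.

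**What the trial's own data can give.** A two-sided 95% paired-t interval with n = 10 has half-width 2.262/√10 = 0.715 of the observed SD of change. If the mean change were 1.0 SD, the lower limit would be 1.0 − 0.715, about 0.28 SD. A retest gain of that size or more would overturn a conclusion of improvement beyond retest gain. This needs no published value.

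**Sensitivity of the repair.** If a mean gain is subtracted but the published value is wrong, the upper tail of the paired t (noncentral t, 9 df, critical value 2.262) is 4.7% or 8.2% when the value is 0.1 or 0.2 SD too low, and 0.6% when it is 0.2 SD too high. If the true SD of differences is k times the published one, the number of 10 exceeding 1.96 by chance is 10 × [1 − Φ(1.96/k)]: 0.07 for k = 0.8, 0.58 for k = 1.25 and 0.96 for k = 1.5.

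**The case against.** **It is a pilot that admits its limits.** The Limitations paragraph names small size and the lack of a placebo group and defers to a larger randomised trial. Section 7c seeks improvements or trends and sets no hypothesis test. This stands, and it limits the point: no confirmatory claim is at risk. But the paragraph does not mention retest gain, and naming a limitation does not supply the missing mean.

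**The plan may intend to include a mean.** The yardstick sentence refers to the retest change one would expect, which could cover an average shift. That reading is possible, but the sentence names only an SD and no step of the analysis subtracts anything.

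**The sentence does not mention the group.** The reference to individuals and the group is in a separate sentence about age-normed change. This stands, so the group figures apply only if the rule is used on the mean.

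**No gain is shown to exist.** This also stands. The documents give no evidence on its size over six months in this population, and with no gain the rule shown is correctly sized.

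**Picture Vocabulary could act as a check.** Section 4a calls it less likely to respond to treatment, but no section uses it to estimate or remove a retest effect.

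A reader might go further in two ways that the documents do not support:
- One might infer that the rule could equally miss a real effect. That requires holding the group mean against an SD not scaled for n, which the plan nowhere says it will do. Nor does it propose a test of the mean against zero.
- One might infer that none of the cited publications gives an average retest change. The Toolbox papers cited in section 4a may do so. The documents show only that section 7c does not say which source it will use.

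**Conclusion.** The point holds in a limited form and is worth fixing. In a study without a control group, the only stated yardstick for retest change is a measure of spread. An average retest gain, if there is one, would therefore be counted as change on drug, in individuals and, if the rule is applied to the mean, in the group.

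The size depends wholly on assumed values. Under the scaled 1.96 SD group rule, the upper-tail error rises from 2.5% to between 9% and 35% for gains of 0.2 to 0.5 SD. At a 1.96 SD individual cut-off, expected false improvers rise from 0.25 to 0.72 of 10 for a gain of 0.5 SD. These figures assume normality, an inert drug and a published SD of differences that fits this population. They do not show that a gain exists or that the trial's result will be wrong.

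**What to change.** In section 7c:

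1. **Group.** Report the mean change in the age-corrected primary score with a two-sided 95% paired-t interval from the trial's own SD. Compare it with a cited published mean retest gain, not with zero or with an SD. Report the lower limit as the retest gain at which the conclusion would reverse.
2. **Individuals.** Use (change − published mean gain) / published SD of retest differences, not a standard error of measurement, with one stated cut-off. Report the number exceeding it beside the number expected by chance (0.25 of 10 at +1.96, if the published SD applies).
3. **Score.** Take the published mean and SD for the same score as the primary outcome. Reconcile List Sorting alone (section 4a) with the combined score (section 7a) on scientific grounds; which score happens to have published retest values should not decide the endpoint.
4. **Timing.** State whether the score and cut-off were fixed before or after any interim look at outcomes. Section 7c plans one at one year and the Milestone Table dates a go/no-go analysis of participants 1 to 5 to February 2020, while the document is dated 29 June 2021.

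The cost is a paragraph of text and a few lines of analysis, with no new participant data. It does need a published mean and SD, which the documents do not show to exist; the reversal point in item 1 works without them. The drawback is that published values may not transfer to cognitively impaired participants aged 3 to 50 tested remotely six months apart. Keep one primary reference value and show a labelled sensitivity range of gains and SDs around it.

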Those who do not demonstrate a clear benefit after six months of treatment will be weaned off of the study drug over a month, and seen back for one final follow-up visit one month later. All subjects removed early from the study will be requested to complete the end of study assessments while still on study drug; but only if safely possible and with subject consent.

At study's end, any patient doing well on Epidiolex and demonstrating improvement on cognitive, neurologic, mood and/or behavioral assessments may continue on the drug (extension study). Every effort will be made to obtain insurance authorization based on the cognitive and medical improvements

demonstrated by the trial; if required the drug will be provided free of cost to the subject until the drug is approved for clinical use for the treatment of cognitive impairments (or other measured indications) in patients with Sturge-Weber syndrome.

They will then be followed and seen about every 3 months, at which time interim history, including evaluation of side effects and patient reported outcomes, neuroscore, photographs of the port wine birthmark, and the Neuroquality of Life questionnaire will be collected. During the extension phase, the PI will have the ability to change dose (increase and decrease) dose of Epidiolex and other anti-seizure medications as clinically indicated. The maximum dose of Epidiolex will not exceed 20 mg/kg/day. The extension study will consist of at least 4 visits, with the option to remain on the extension study until insurance company approval is obtained for Epidiolex. Study drug will be provided by Greenwich Biosciences until insurance coverage is obtained. The study coordinator will contact the family once per month to ensure the subject is taking the Epidiolex. The study coordinator will ask how much of the Epidiolex the subject has remaining and will ask to see the bottle(s) to confirm.

Lab work (CBC, anticonvulsant levels, and chemistries about every 3 months) will be done as part of clinical care. At all extension study visits, there will be a urine pregnancy test. If the subject is under the age of 18, these results will be given to the parents.

Every six months, an interim analysis will be done of adverse events and outcome measures. Results will be discussed by the Research Investigators and a summary sent to Greenwich Biosciences.

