The enrolled subjects have cognitive impairments that affect their ability to independently receive education or to work. Epidiolex may have positive effects on SWS cognitive problems, social impairments, mood, migraines, or motor function. If successful, this study would lay the foundation for a completely new treatment option for patients with SWS and cognitive impairment. It is likely that this study will result in new information regarding the usefulness of Epidiolex for Sturge-Weber syndrome cognitive impairments and other neurologic issues.

10. Payment and Remuneration

a. Detail compensation for participants including possible total compensation, proposed bonus, and any proposed reductions or penalties for not completing the protocol.

There will not be any financial remuneration for subject participation in this phase II trial. There will also not be any penalty for not completing the study. Any decisions to not participate or to withdraw will not affect the patient's care.

11. Costs

a. Detail costs of study procedure(s) or drug (s) or substance(s) to participants and identify who will pay for them.

The study drug and study funding will be provided by Greenwich Biosciences. The costs of the motor testing will be covered by funding provided by the Faneca 66 Foundation..

Limitations: The main limitations of this study are its size and lack of a placebo group. However at this point, when the best outcome measures for assessing the improvements need to be ascertained, the proposed trial is most appropriate. A larger, randomized, placebo-controlled trial can be done after this trial is completed. All of the outcome measures proposed are familiar to the investigators; most of them have previously been utilized here in subjects with SWS. [name] has previously successful drug trials in SWS and is expected to successfully complete the proposed drug trial.

References

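### Section 7c says 10 open-label, uncontrolled subjects are enough to inform patient care, but no calculation, interval or definition of a trend supports this

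*Combined protocol and SAP*

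**What the plan says.** Under Sample Size Calculation, Section 7c states that "a sample size calculation was not done". It goes on to estimate that "10 subjects enrolled and on study drug will be sufficient to do the proposed pilot trial" and to "show improvements (or trends for improvement) sufficient to design a future larger clinical trial, or to guide clinical care". The only basis offered is: "This estimate is based on our experience with another trial using the same primary outcome measure". No figure from that other trial is given.

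The Statistical Plan in the same section says: "Mean and standard deviation of this difference for all 10 subjects on study drug will be calculated". No test, confidence interval or significance level is named. Results are also to be set against age norms, and published test-retest SDs are to show whether changes go beyond what retesting alone would produce. How many SDs are required is not stated, nor whether the comparison is for each subject, for the group mean, or both. The section adds: "There is no control group in this study of subjects who are not receiving study drug". Section 4c says the trial is not blinded.

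The Limitations paragraph at the end of Section 11 concedes small size and lack of placebo. It defends the design on the ground that "when the best outcome measures for assessing the improvements need to be ascertained, the proposed trial is most appropriate", and says a randomized placebo-controlled trial can follow.

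The primary outcome is given in two ways. It is the List Sorting Working Memory score alone under Outcome Measures in Section 4a, and a combined score of two NIH Toolbox subtests in Section 7a.

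**The concern.** A sample size can be justified by the precision it gives or by the effect it can detect. Here it is justified by an expected favourable result, which may be no more than a trend, and that result is said to be enough for two different uses. Helping to design a controlled trial is a fair aim for ten subjects. Informing patient care is not, when the result comes from an unblinded before-after comparison with no control and no stated precision.

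Two things are at stake. An imprecise mean change could be presented as grounds for treatment because the plan said in advance that this would suffice. And the next trial could be planned on an SD that ten subjects estimate poorly, with nothing in the plan to warn of it.

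**Working it through.** **Inputs from the document.** n = 10 on study drug, single arm, each subject as own control (Sections 4a and 7c). No alpha, power, effect size or SD of change is given, so the figure of 10 cannot be reproduced. Everything below is in units of the SD of the change score and assumes roughly normal changes.

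**Precision of the mean change.** The 95% CI half-width is t(0.975, 9)/√10 = 2.262/3.162 = 0.715 SD.

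**Detectable change.** For a two-sided 5% paired t-test with 9 df and noncentrality d√10, power reaches 80% at d = 0.996. Power is 14% at d = 0.3, 29% at d = 0.5 and 62% at d = 0.8.

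**Precision of the SD.** The 95% limits for the true SD, as multiples of the estimate, are √(9/χ²) with 9 df: √(9/19.02) = 0.69 and √(9/2.70) = 1.83. Sample size scales with the variance, so the factor for a next trial runs from 0.69² ≈ 0.47 to 1.83² ≈ 3.3.

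These three results do not depend on how a trend is read. The next two depend on readings that the plan leaves open.

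**What the test-retest yardstick could mean if nothing changes.** Assume that the published SD is that of a difference score and applies to this population.

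| Reading | Chance of passing with no true change |
|---|---|
| Group mean above 1 SD: 1 − Φ(√10) | 0.08% |
| Group mean above 1.96 standard errors | 2.5% |
| A given subject above 1 SD: 1 − Φ(1) | 15.9% |
| At least one of 10 subjects above 1 SD: 1 − (1 − 0.159)^10 | 82% |

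If the true SD of change in this population were twice the published one (an assumption), the first row would become 1 − Φ(√10/2) = 5.7%.

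**What a trend could mean on the primary if nothing changes.**

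- Any positive mean, with no practice or expectancy gain: 50%.
- Any positive mean, with an assumed gain of 0.1, 0.2 or 0.3 SD: Φ(gain × √10) = 62%, 74% or 83%.
- At least 7 of 10 subjects improved: 17%.
- One-sided p < 0.10: 10%.

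**Any of several outcomes, loosest reading only.** Sections 7a and 7b list one primary and seven secondary lines; leaving out adverse events gives seven headings. If these were independent, the chance of at least one positive mean is 1 − 0.5^7 = 99%. With a common correlation ρ it is 1 − ∫φ(u)Φ(−u√ρ/√(1−ρ))^7 du, which gives 94% at ρ = 0.3, 88% at 0.5 and 79% at 0.7. The correlations are assumed. Some overlap is certain, because the neuroscore in Section 4a includes seizure, hemiparesis and cognitive components.

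**The case against.** The strongest defence is that the plan does contain a yardstick. A change within test-retest error would be a negative result under Section 7c, and at group level an inert drug would rarely pass (0.08% or 2.5% above). The Milestone Table also schedules a Go/No Go decision after subjects 1 to 5, though without a criterion. A reader might therefore infer too much in saying that there is no threshold, or that the trial cannot come out negative. The documents do not support either statement; what they support is that the rule is too vague to apply.

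A reader might also infer that an inert drug meets the plan's bar half the time on the primary and almost always on something. The sample size sentence sets no success criterion. The 50% holds only if any positive mean counts, and the 99% also needs independent outcomes, which seven measures on the same ten people will not be.

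Nor does any section say that the next trial will be sized on whichever outcome moved most. The Limitations paragraph says only that the best measures are still to be found, and Section 4a names a primary in advance. In the extension section, "Every effort will be made to obtain insurance authorization based on the cognitive and medical improvements" concerns continued access for patients who are doing well. It does not say that a group trend is enough.

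Finally, wide intervals are a feature of any ten-subject pilot, and the plan concedes its size and lack of placebo. That stands, and is why n = 10 itself is not the complaint. The concession does not withdraw the sufficiency claim in Section 7c, however, and the two sit badly together.

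**Conclusion.** The point holds in this form: the claim that ten subjects will suffice to inform patient care has no support in the plan, and the analysis that would have to bear it is under-specified. The firm figures are the ±0.72 SD interval, 80% power only near a 1.0 SD change, and the 0.47 to 3.3 range for a next-trial sample size. They rest on n = 10 complete pairs and approximate normality.

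The chance of a spurious trend cannot be fixed at one number, because the plan defines no trend. On the loosest reading it is 50% for the primary without drift, and 79% to 99% for at least one of seven headings at assumed correlations of 0.7 down to 0. Practice or expectancy gains would raise the 50%, and this design cannot separate them from a drug effect.

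This should be corrected. It changes what the trial may conclude, not whether it is worth doing.

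**What to change.** 1. Reconcile Sections 4a and 7a on the primary outcome. No threshold or interval can be set until this is done.
2. In Section 7c, delete the parenthesis about trends and the closing clause about clinical care. Say instead that n = 10 gives a 95% CI half-width of 0.72 SD of change and is meant to inform the design of a controlled trial. If the other trial that the plan cites yields an SD of change for the chosen primary, convert the half-width to score points; whether such an SD exists is not stated.
3. Report the mean primary change with its 95% CI against the expected no-drug retest change, naming the source of that reference. Judge the group by the standard error of the mean, and use the published test-retest SD only for individual subjects, with the multiple stated.
4. Report every other outcome with a 95% CI and label it exploratory. State that the next trial will not be sized on the largest observed change.

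The cost is a change of wording and a few added intervals. The promise made for the trial becomes less favourable. No extra patients, visits or measurements are needed. The intervals will describe sampling error only and will not make up for the missing control group, so the text should say that too.
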